### 4. STUDY DESIGN

### 4.1. Overall Design

This is a Phase 1, open-label, single-dose, randomized 4-crossover periods and 1-fixed period design in a single cohort of approximately 16 healthy male or female participants .

The study will consist of 5 treatments as shown below:

- 1. Treatment A: Single oral dose of etrasimod 2 mg clinical IR tablet under fasted conditions (Reference)
- 2. Treatment B: Single oral dose of etrasimod 2 mg mini tablets mixed with applesauce under fasted conditions (Test 1)
- 3. Treatment C: Single oral dose of etrasimod 2 mg mini tablets mixed with chocolate pudding under fasted conditions (Test 2)
- 4. Treatment D: Single oral dose of etrasimod 2 mg mini tablets mixed with water under fasted conditions (Test 3)
- 5. Treatment E: Single oral dose of etrasimod 2 mg mini tablets mixed with yogurt under fasted conditions (Test 4)

Sixteen participants will be enrolled in Period 1 for a total of 12 evaluable participants to complete study. Participants will be randomly assigned to 1 of the 4 sequences shown in Table 2 in which participants are randomized in crossover design to receive Treatments A to D in Periods 1 to 4 with Treatment E being fixed in Period 5. Participants will be discharged on Day 9 of Period 5, following completion of all assessments. Each treatment is 9 days that includes dosing, PK sampling and an extra day to minimize any residual etrasimod concentrations prior to start of the next treatment. The total planned duration of participation from the screening visit to the last follow-up phone call, is approximately 14 weeks.

Treatment sequence (n=4 per sequence)	Period 1	Period 2	Period 3	Period 4	Period 5 (fixed)
1	А	В	С	D	Е
2	В	D	А	С	Е
3	С	А	D	В	Е
4	D	С	В	А	Е

 Table 2.
 Treatment Sequence

Since etrasimod has a half-life approximately 30 hours, there will be a 9-day washout between each dose.

Blood samples for PK analysis will be collected predose and at 1, 2, 4, 6, 8, 12, 24, 48, 72, 96, 120, 144 and 168 hours postdose (SoA). Capillary blood samples (using micro sampling Tasso device) will be collected at predose and at 1, 2, 4, 6, 8, 12 and 24 hours postdose (SoA) for PK assessments (Treatment A). Micro PK sampling occurs after PK blood sampling, and taken from the other arm.

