A palatability assessment will be conducted during which a palatability assessment questionnaire will be completed for the sprinkled mini tablets in every period, with 1 minute (immediately after dosing), before administered the water up to a total volume of 240 mL, and at 5 minutes, 10 minutes, 20 minutes after dosing is fully completed. Additionally, participants will be asked to not verbalize their responses and not discuss palatability with other participants until after they have filled out the responses in the questionnaire.

Participants will participate in the study up to approximately 3.5 months, with the inclusion of the screening and follow-up period. Participants will be screened within 28 days of the first dose of study intervention and if all entry criteria are fulfilled, the participants will report to the CRU on the day prior to Day 1 dosing (Day -1). On Day 1 of each period, participants will receive a single dose of study intervention. Administration of etrasimod will be oral via dosing of clinical IR tablet 2 mg or mini tablets 2 mg (as  $16 \times 0.125$  mg) with water or on soft foods as per dosing instructions. Participants will be fasted for at least 10 hours predosing and 4 hours postdosing.

Participants will be confined in the CRU for a total of at least 45 days and discharged at the discretion of the investigator. A follow-up phone call will be made at least 28 calendar days and up to 35 calendar days after the last administration of the study intervention to capture any potential AEs and confirm appropriate contraceptive usage.

Tolerability and safety will be assessed for all treatments by monitoring AEs. Participants who withdraw from the study or whose PK samples are determined to be non-analyzable may be replaced at the discretion of the of the investigator upon consultation with the sponsor.

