### 6.1.1. Administration

On Day 1 of each period, following an overnight fast of at least 10 hours, participants will receive study intervention at approximately 0800 hours (plus or minus 2 hours). Investigator site personnel will administer study intervention during each period.

Etrasimod clinical IR tablets will be administered with ambient temperature water to a total volume of approximately 240 mL.

Etrasimod mini tablets will be administered mixed with 5 mL of either applesauce, chocolate pudding, yogurt or water followed by approximately 235 mL of ambient temperature water or by 5 ml rinsing if dispersion in water followed by 230 ml water. See IPM for detailed instructions on preparation and administration of study intervention.

Participants will swallow the clinical IR tablets whole and mini tablets mixed with applesauce, chocolate pudding, yogurt, or water, and will not manipulate or chew the study intervention prior to swallowing.

In order to standardize the conditions on PK sampling days, all participants will be required to refrain from lying down (except when required for ECG measurements), eating, and drinking beverages other than water during the first 4 hours after dosing.

Administration of study intervention(s) will be performed by an appropriately qualified and trained member of the study staff as allowed by local, state, and institutional guidance.

Following administration of study intervention(s), participants will be observed for the complete period/study by an appropriately qualified and trained member of the study staff.

Appropriate medication and other supportive measures for management of a medical emergency will be available in accordance with local guidelines and institutional guidelines.

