#### 8.10. Palatability Assessments

Palatability assessment of the etrasimod mini tablets will be conducted in every period for Treatments B, C, D, E with the aid of a questionnaire (Appendix 9). The palatability assessment questionnaire will be administered to participants by trained staff using a colored copy of the questionnaire. After study intervention administration, participants will be asked to rate the mouth feel, bitterness, tongue/mouth burn, throat burn, and overall liking. The participants will rate the above within 1 minute (immediately) after dosing, before drinking water that is given as part of dosing, and at 5 minutes, 10 minutes, 20 minutes after dosing is fully completed.

See Appendix 9 for the details about the palatability assessment questionnaire.

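### The instruction not to discuss palatability lapses after each period's questionnaire, so peer opinion can reach 36 of the 48 applesauce, pudding and water ratings

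*Protocol*

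**What the plan says.** Protocol Section 4.1 tells participants not to voice their responses and to "not discuss palatability with other participants until after they have filled out the responses in the questionnaire". Section 8.10 says that the assessment "will be conducted in every period for Treatments B, C, D, E with the aid of a questionnaire", with the later ratings "at 5 minutes, 10 minutes, 20 minutes after dosing is fully completed". The Appendix 9 form carries a field for period and day, so one form belongs to one period.

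On the setting, Section 4.1 describes a study "in a single cohort of approximately 16 healthy male or female participants" and adds: "Participants will be confined in the CRU for a total of at least 45 days". Participants "receive Treatments A to D in Periods 1 to 4 with Treatment E being fixed in Period 5". Section 6.4 states that the study is open-label.

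Palatability is a secondary objective (Section 3). Section 2.3 names palatability data among those the study is designed to generate in support of later pediatric studies. Protocol Section 9.3.4 and SAP Section 6.2.2 plan listings, descriptive summaries, means with 90% CIs and radar plots.

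The Schedule of Activities (SoA), Section 8.10, Appendix 9, and SAP Sections 3.2.2 and 6.2.2 contain no restriction on discussion between periods.

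**The concern.** The instruction shows that the sponsor regards peer opinion as a possible influence on the scores. As worded, it protects a participant's own rating in the current period but not the later ratings of others. In a study where everyone tasted the same product once, at the same time, that would be enough. Here three vehicles rotate, so someone who has finished with applesauce in Period 1 may describe it freely to people who will receive it in Periods 2, 3 or 4.

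The scores are subjective marks on a color bar, and participants know what they are taking. If opinions spread, later ratings of a vehicle would partly reflect what others said about it. The analysis could not correct for this, because neither document provides for recording who spoke to whom.

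**Working it through.** No power or precision formula applies. The check is a count from Table 2 of the protocol.

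**Inputs**
- Sequences (Table 2): 1 = A B C D E; 2 = B D A C E; 3 = C A D B E; 4 = D C B A E.
- Four participants per sequence (Table 2). The plan's own total reproduces: 4 × 4 = 16.
- Rated treatments: B (applesauce), C (pudding), D (water), E (yogurt). A is not rated (Section 8.10).
- One rating means one participant's questionnaire for one vehicle, so there are 16 × 4 = 64 ratings, of which 16 × 3 = 48 are for B, C and D.

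**Definition.** A rating is open to peer opinion if another sequence received the same vehicle in an earlier period.

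**Period in which each vehicle is given**

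| Vehicle | Seq 1 | Seq 2 | Seq 3 | Seq 4 |
|---|---|---|---|---|
| B | 2 | 1 | 4 | 3 |
| C | 3 | 4 | 1 | 2 |
| D | 4 | 2 | 3 | 1 |
| E | 5 | 5 | 5 | 5 |

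For each of B, C and D, one sequence (4 participants) tastes it in Period 1 and three sequences (3 × 4 = 12 participants) taste it later. For E, no sequence tastes it before another.

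**Count by period**

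| Period | Ratings | Open to peer opinion |
|---|---|---|
| 1 | 12 | 0 |
| 2 | 12 | 12 |
| 3 | 12 | 12 |
| 4 | 12 | 12 |
| 5 | 16 | 0 |
| Total | 64 | 36 |

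**Result**
- B, C and D: 3 × 12 = 36 of 48 = 75%.
- All four vehicles: 36 of 64 = 56.25%.
- With the 12 evaluable completers of Section 4.1, if 3 per sequence: 3 × 9 = 27 of 36 for B, C and D (75%), and 27 of 48 overall (56.25%). The proportions do not change.

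**After the change.** If the instruction ran to the end of the Period 5 ratings and were fully followed, the count would fall from 36 to 0. That is the limiting case, not a forecast.

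**The case against.** The strongest reply is that these are counts of opportunity, not of bias. A reader might infer that most ratings are contaminated. The documents do not support that: they show only that later talk is not barred, and they give nothing from which to estimate a shift on the 0 to 100 scale. This stands.

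Three further inferences are tempting and also go too far:

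- **Same-morning talk, including about yogurt.** Section 6.1.1 allows dosing at 0800 plus or minus 2 hours, so one might argue that early finishers can brief those not yet dosed. But this is a tolerance around a nominal time, not a stated stagger. The pronoun in "not discuss palatability with other participants until after they have filled out the responses in the questionnaire" can also be read as the whole group or as the other participants, in which case same-morning talk is already barred. The between-period gap survives these readings unless the questionnaire is also stretched to mean every later period's form, which nothing in the text suggests.
- **Invalid 90% CIs.** Shared opinions could correlate the ratings, but the size of any correlation is unknown. The intervals are descriptive, and no hypothesis or decision rule depends on them (SAP Sections 5.1 and 6.2.2).
- **An unfair comparison with yogurt that this change would repair.** Applesauce, pudding and water have equal exposure, 12 of 16 each. Yogurt differs, but it is confounded with Period 5 and with three earlier personal tastings of the mini tablets, whatever is done about discussion. No between-vehicle contrast is planned.

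It is also fair to say that the pre-dose review of the questionnaire and instructions in the SoA may include a wider briefing that the documents do not show. A restraint lasting weeks among people living together is hard to enforce. Both points limit what can be claimed, but neither supplies the missing instruction.

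**Conclusion.** The gap is real, and closing it is a cheap improvement, not a correction of a serious flaw. The counts above rest on the full 16 (or an even 3 per sequence) moving through the periods together and being free to mix. The single cohort and continuous confinement suggest this, but the documents do not state it. Replacement participants, whom Section 4.1 allows, could follow a different calendar and alter the counts.

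What follows is that peer opinion can influence an open-label, self-rated secondary endpoint, to an unknown extent. The primary endpoints (AUC and Cmax) are untouched.

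**What to change.** In Sections 4.1 and 8.10, change where the instruction ends: ask participants not to discuss the taste, mouth feel or liking of any treatment with other participants until those in the CRU have completed their Period 5 20-minute questionnaire. Tying the end to those in the CRU avoids making discharged participants wait for a late replacement. Repeat the instruction at the pre-dose questionnaire review already in the SoA for each mini-tablet period.

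The cost is one sentence in each section and a line in the site instructions. Sample size, schedule, dosing and staffing do not change.

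The downside is imperfect adherence: Period 1 dosing is on study Day 1 and Period 5 dosing on Day 37, so the restraint must hold for 36 days, about 5 weeks. Partial adherence would still be no worse than a rule that leaves the discussion open. The change does not separate yogurt from Period 5 or from participants' own earlier tastings, and the report should say so when the vehicles are shown side by side.

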# 4.2. Scientific Rationale for Study Design

Etrasimod mini tablet is an alternative formulation suitable for pediatric patients who are not able to swallow etrasimod 2 mg clinical IR tablets. The mini tablets are formulated in strength of 0.125 mg that can be sprinkled on soft foods for administration to pediatric UC patients. Study C5041034 will be conducted in healthy adult participants to evaluate the PK of etrasimod mini tablets 2 mg (as  $16 \times 0.125$  mg) dissolved in water or soft foods (applesauce, chocolate pudding and yogurt [Test]) in comparison to etrasimod clinical IR tablet (Reference) in fasted state. Furthermore, a palatability assessment will be conducted with the mini tablets in soft foods.

# 4.2.1. Rationale for ECG Measurements

In the heart, S1P1 is expressed on atrial myocytes and is associated with the regulation of heart rate. S1P1 agonism activates both G alpha i (Gi) and  $\beta$ -arrestin signaling pathways.  $\beta$ -arrestin activation leads to receptor internalization, while Gi coupled signaling activates GIRK channels that regulate potassium efflux and membrane potential. As a result, there is a transient, first dose associated, chronotropic (slowing of HR) and dromotropic (slowing of AV nodal conduction) effects associated with etrasimod (a class effect). For all Phase 1 studies, intensive ECG have been taken for the first 6-hours post first dose. For this study, this practice should be in place until the NDA is approved.

# 4.2.2. Rationale for PR and BP Monitoring

In addition to the transient, first dose associated, chronotropic effect associated with etrasimod, hypertension has been observed with S1P receptor modulators and AEs of hypertension have been reported. For all phase 1 studies, intensive BP and PR monitoring post dose has been undertaken and this will continue for this study.

# 4.2.3. Rationale for Micro Sampling

Etrasimod will be evaluated in children as young as 2 years old in a future pediatric study (C5041018) in which IV blood draw may be challenging. This is designed to validate etrasimod PK concentrations in capillary blood collected using the Tasso device against PK samples collected from traditional venous blood samples. Findings from the validation will enable patient-centric blood sampling using this innovative device in future etrasimod pediatric clinical studies.

# 4.2.4. Choice of Contraception/Barrier Requirements

Etrasimod is known to cause risk for severe manifestations of developmental toxicity in humans or suspected on the basis of the intended pharmacology. Therefore, the use of a highly effective method of contraception is required for both female and male participants (see Appendix 4).

# 4.3. Justification for Dose

The dose of etrasimod 2 mg once daily has been shown to be efficacious and safe in moderate to severely active adult UC patients.

This study is designed to evaluate rBA of etrasimod 2 mg mini tablets (as  $16 \times 0.125$  mg) with water or 3 food vehicles compared to etrasimod 2 mg clinical IR tablet formulation in healthy adult participants. The projected doses in pediatric study utilizing mini tablets range from 0.5 mg to 1.5 mg. The dose selected for pediatric participants based on age and body weight is intended to generate exposures (AUC) to match adult exposures following etrasimod 2 mg.

# 4.4. End of Study Definition

The end of the study is defined as the date of the last visit of the last participant in the study or last scheduled procedure shown in the SoA and the investigator has reviewed the final safety data and determined that no additional evaluation is required.

A participant is considered to have completed the study if they have completed all periods of the study, including the last visit or the last scheduled procedure shown in the SoA.

# **5. STUDY POPULATION**

This study can fulfill its objectives only if appropriate participants are enrolled, including participants across diverse and representative racial and ethnic backgrounds. If a prescreening tool is utilized for study recruitment purposes, it will include collection of information that reflects the enrollment of a diverse participant population including, where

permitted under local regulations, age, sex, race, and ethnicity. The following eligibility criteria are designed to select participants for whom participation in the study is considered appropriate. All relevant medical and nonmedical conditions should be taken into consideration when deciding whether a particular participant is suitable for this protocol.

Prospective approval of protocol deviations to recruitment and enrollment criteria, also known as protocol waivers or exemptions, is not permitted.

### 5.1. Inclusion Criteria

Participants are eligible to be included in the study only if all of the following criteria apply:

### Age and Sex:

- 1. Male and female participants aged 18 years or older (or the minimum age of consent in accordance with local regulations) at screening who are overtly healthy as determined by medical evaluation including a detailed medical history, full physical exam, which includes BP and pulse rate measurement, clinical laboratory tests, temperature, and 12-lead ECG.
  - Refer to Appendix 4 for reproductive criteria for male (Section 10.4.1) and female (Section 10.4.2) participants.

## **Other Inclusion Criteria:**

- 2. BMI of 16 to 32 kg/m^2; and a total body weight > 50 kg (110 lb).
- 3. Participants who are willing and able to comply with all scheduled visits, treatment plan, laboratory tests, lifestyle considerations, and other study procedures.
- 4. Capable of giving signed informed consent as described in Appendix 1, which includes compliance with the requirements and restrictions listed in the ICD and in this protocol.

# 5.2. Exclusion Criteria

Participants are excluded from the study if any of the following criteria apply:

# **Medical Conditions:**

1. Evidence or history of clinically significant hematological, renal, endocrine, pulmonary, gastrointestinal, cardiovascular, hepatic, psychiatric, neurological, anaphylactic, ophthalmologic disorders (such as macular edema, uveitis, retinopathy),

or allergic disease (including drug allergies, but excluding untreated, asymptomatic, seasonal allergies at the time of dosing).

- Myocardial infarction, unstable angina, stroke/transient ischemic attack, decompensated heart failure requiring hospitalization, or Class III/IV heart failure ≤8 weeks prior to study treatment
- Second- or third-degree AV block, sick sinus syndrome without a functional pacemaker, or periods of asystole for >3 seconds without an implanted cardiac defibrillator
- Recurrent symptomatic bradycardia or recurrent cardiogenic syncope
- History of congenital long QT syndrome
- Other medical or psychiatric condition including recent (within the past year) or active suicidal ideation/behavior, laboratory abnormality or other conditions that may increase the risk of study participation or, in the investigator's judgment, make the participant inappropriate for the study
- 2. Any condition possibly affecting drug absorption (eg, gastrectomy, cholecystectomy).
- 3. Known immunodeficiency disorder, including positive serology for HIV, or a first degree relative with a hereditary immunodeficiency.
- 4. Infection with hepatitis B or hepatitis C viruses according to protocol specific testing algorithm history.
  - For hepatitis B, all participants will undergo testing for HbsAg and HbcAb.
  - If HbsAg is positive, the participant must be excluded from participation in the study.
  - If HbsAg and HbcAb are both negative, the participant is eligible for study inclusion.
  - If HbsAg is negative and HbcAb is positive, HbsAb should be evaluated:
  - If HbsAb is negative, the participant must be excluded from participation in the study;
  - If HbsAb is positive, the participant is eligible for study inclusion.
  - For hepatitis C, all participants will undergo testing for HCVAb. Only participants who are HCVAb negative are eligible.
- 5. Participants with any of the following acute or chronic infections or infection history:
  - Any infection requiring treatment within 2 weeks prior to dosing.

- Any infection requiring hospitalization or parenteral antimicrobial therapy within 60 days of the first dose of study intervention.
- Any infection judged to be an opportunistic infection or clinically significant by the investigator, within the past 6 months of the first dose of study intervention.
- Known active or history of recurrent bacterial, viral, fungal, mycobacterial or other infections.
- History of recurrent (more than one episode of) localized dermatomal herpes zoster, or history of disseminated (single episode) herpes simplex or disseminated herpes zoster.
- History of febrile illness within 5 days prior to the first dose of study intervention.
- 6. History of any lymphoproliferative disorder such as EBV related lymphoproliferative disorder, history of lymphoma, history of leukemia, or signs or symptoms suggestive of current lymphatic or lymphoid disease. Known present or a history of malignancy other than a successfully treated or excised nonmetastatic basal cell or squamous cell cancer of the skin or cervical carcinoma in situ.
- 7. Evidence of untreated or inadequately treated active or latent Mycobacterium TB infection as evidenced by the following:
  - A positive QFT-G test performed within the 12 weeks prior to screening. If the laboratory reports the test as indeterminate, the test should be repeated. If the result of the repeat test is indeterminate, a PPD test may be substituted for the QFT-G test only with approval from the Pfizer Medical Monitor on a case-by-case basis.
  - History of either untreated or inadequately treated latent or active TB infection.
  - If a participant has previously received an adequate course of therapy for either latent (9 months of isoniazid in a locale where rates of primary multi-drug resistant TB infection are <5% or an acceptable alternative regimen) or active (acceptable multi-drug regimen) TB infection, neither a QFT-G test nor a PPD test need be obtained. Details of the previous course of therapy (eg, medication(s) used, dose, duration of therapy) should be documented in the source documentation.
  - A participant who is currently being treated for active or latent TB infection must be excluded from the study.
- 8. Participants with ANY of the following abnormalities in clinical laboratory tests at screening or Day -1, as assessed by the study-specific laboratory and confirmed by a single repeat test, if deemed necessary:

WBC <3500/mm^3 (<3.5 × 10^9 cells/L) PFIZER CONFIDENTIAL CT02-GSOP Clinical Pharmacology Protocol Template (14 April 2023) Page 33

- ANC <1500/mm^3 ( $<1.5 \times 10^9$  cells/L)
- ALC  $< 800/\text{mm}^3$  ( $< 0.8 \times 10^9$  cells/L)
- Platelet count  $<100/\text{mm}^3$  ( $<100 \times 10^9$  cells/L)
- Hemoglobin <10 g/dL
- AST or ALT level > ULN;
  - Total bilirubin level > ULN; participants with a history of Gilbert's syndrome may have direct bilirubin measured and would be eligible for this study provided the direct bilirubin level is ≤ ULN;
  - eGFR <60 mL/min/1.73 m^2 based on the CKD-EPI equation. Based upon participant age at screening, eGFR or eCrCl is calculated using the recommended formulas in Section 10.6.2 to determine eligibility and to provide a baseline to quantify any subsequent kidney safety events. For eligibility assessment based upon estimated renal function, the higher of the screening and baseline eGFR values may be used.
  - In the opinion of the investigator or Pfizer (or designee), have any clinically significant laboratory abnormality that could affect interpretation of study data or the participant's participation in the study.

